6.8.2 Other pharmacodynamic endpoints analysis

6.8.2.1 Variables

Endpoints

Other PD endpoints include the following:

- **Extent of aggregation:** maximum platelet aggregation (MAP; %), final platelet aggregation (FPA; at 6 minutes, %) as measured by light transmission platelet aggregometry (LTA).

- **Absolute PRU values (for VerifyNow®) at each measured time point.**
- % of subjects at 8 h after study treatment injection with PRU value < 100 or $< 0.95 \times \text{PRU baseline value}$ if PRU baseline < 100 (i.e., platelet aggregation status 8 hours after study drug administration).

The following exploratory endpoints will also be considered in the PD analysis:

- IPA (noted IPA-V) as measured by VerifyNow®, data for this endpoint will be available only for some centers.

A supportive PD endpoint is defined in the protocol statistical section for LTA-PD response. However, the exact definition of the endpoint is not provided. Therefore, the following definition will be considered for defining LTA-PD response: an IPA-M of at least 50% starting 30 minutes after injection, lasting at least 3 hours, and not exceeding the 8th hour after study drug administration for subjects with value above.

Variables

The variable of *extent of aggregation* (MPA) is used as reported in the eCRF, and is expressed as a percentage.

The *absolute PRU* variable is the actual PRU value as reported by VerifyNow®, at each time point [see protocol table 2 and table 3], and is expressed as a number without unit (the higher the number, the less IPA).

The *subject platelet aggregation status 8 hours after study drug administration* variable is defined as binary with value determined as per the following algorithm:

IF ($\text{PRU}_{\text{baseline}} \geq 100$ AND $\text{PRU}_{8h} < 100$) OR ($\text{PRU}_{\text{baseline}} < 100$ AND $\text{PRU}_{8h} < 0.95 \times \text{PRU}_{\text{baseline}}$)
THEN status = YES
ELSE status = NO

The variable of the *IPA by VerifyNow®* (IPA-V) is the value reported in the eCRF, and is expressed as a percentage. All analyses conducted on this variable will exclude missing values.

The LTA-PD response variable is defined as:

IF minimum of (IPA-M_{30m} , IPA-M_{4h}) $\geq 50\%$
AND none is missing
THEN LTA-PD response = YES
ELSE LTA-PD response = NO

The variable *IPA-M at time t* (noted IPA-M_t) is expressed as a percentage, and defined as:

$$\text{IPA-M}_t = (1 - \text{MPA}_t / \text{MPA}_{\text{baseline}}) \times 100.$$

Where MPA_t is MPA at time t after study drug administration, and $MPA_{baseline}$ is the latest MPA value reported up to randomization.

MPA and FPA are measured twice at each point, for the analysis, the average of the two assessments will be used for each time point.

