5 TREATMENTS

5.1 Study treatment

5.1.1 Investigational treatment and matching placebo: Description and rationale

Study treatment for s.c. administration will be available as sealed glass vials in 1 strength: 20 mg. The vials contain 22 mg of lyophilized ACT-246475A (hydrochloride salt of

ACT-246475) or matching placebo to be reconstituted with 1 mL of water for injection. The s.c. formulation contains mannitol as an inactive ingredient.

Study treatment will be given as a single dose, administered s.c. at site by qualified personnel (e.g., nurse, physician).

ACT-246475 at 2 different doses (8 and 16 mg) and placebo will be administered during this study. The ACT-246475 doses have been selected based on data from the SAD AC-076-102 study and on modeling to meet the following criteria:

- The low dose (8 mg) is the minimal dose achieving at least 85% IPA for 3 h which corresponds to a time period during which complete suppression of platelet reactivity is needed before specific in-hospital management of ACS [Montalescot 2014].
- The high dose (16 mg) provides IPA of at least 85% in no more than 5% of the subjects at 8 h. This corresponds to the maximal time accepted to limit interference with invasive and/or pharmacological standard of care of AMI.

These 2 doses are considered distinct enough to allow further modeling of the optimal phase 3 dose based on study data.

Note: onset of action of ACT-246475 is not dose-dependent and therefore did not account for dose selection.

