10.5 Sample size

The sample size is based on the primary PD endpoint, which is the proportion of subjects achieving a predefined PD response as measured by VerifyNow®. The computation of the sample size was performed using the East 6.0 software (version 6.4.0.1, 30 Aug. 2016) from Cytel.

This study includes 3 treatment arms, 2 active arms (ACT-246475 8 mg and 16 mg) and a placebo arm comprising the 2 dose-matching placebo groups.

The primary objective is to assess the effectiveness of ACT-246475 to allow subjects to achieve a predefined PD response, therefore the sample size will be provided in order to reach the necessary power to sequentially demonstrate that at least 1 of the 2 doses has a higher response rate than placebo and that this response rate is statistically significantly greater than the proportion of responders under H_0 .

The sample size required for demonstrating a difference to placebo is based on an overall alpha of 0.05 (2-sided), adjusted for multiplicity using a Bonferroni method to 0.025 for each comparison, and a power of 0.9; the assumptions related to response rate under the null and alternative hypotheses are reported in the table below:

Proportion of responders under H_0 (placebo)	Proportion of responders under H_1 (active)	Number of subjects (total)	Number of subjects (per arm)
50%	75% (odds ratio of 3)	288	96

The sample size required to demonstrate that the achieved response rate is different from 70% is based on a 2-sided type I error (alpha) of 0.025, and a power of 0.9; the assumptions related to response rate under the null and alternative hypotheses, are reported in the table below:

Proportion of responders under H_0	Proportion of responders under H_1	Number of subjects (total for the 2 active arms)	Number of subjects (per arm)
70%	85%	196	98

Therefore the study should include at least 98 subjects evaluable for the primary PD endpoint in each treatment arm. Assuming a rate of drop-out or non-evaluable data of about 10%, each arm will include 108 subjects leading to a total for the study of 324 subjects.

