10.2.2 Baseline

Baseline is the last non-missing assessment performed or value measured before or on the day and time of study drug administration (i.e., prior to treatment administration), unless otherwise defined in the specific analysis section.

Subjects without any data for a parameter before treatment administration will have a missing baseline (and therefore a missing change from baseline) value for this parameter.

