11 CHANGES OR CLARIFICATIONS TO ANALYSES PLANNED IN THE STUDY PROTOCOL

11.1 Changes to the analyses planned in the study protocol

11.1.1 Change in pharmacodynamic variable

The protocol section 10.2.4.2 describes the following PD variable: *% of subjects at 8 h after study treatment injection with PRU value < 100 or > 1.05 × baseline value*.

The intent of this variable was to estimate the proportion of subjects still with a low value of platelet aggregation 8 hours after administration of study drug. This is assuming that a baseline platelet aggregation (PRU_{baseline}) value ≥ 100 .

As some subjects may have a PRU_{baseline} value < 100 , and a PRU_{8h} < 100 , it is not sensible to consider those subjects in the group of subjects with still significantly low platelet aggregation after study drug administration. Unless the PRU_{8h} is lower than PRU_{baseline}.

For this purpose, and to be consistent with the intent of assessing back to normal/baseline value, the definition of this variable should be modified to: *% of subjects at 8 h after study treatment injection with PRU value < 100 or < 0.95 × baseline value*.

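### For subjects with pre-dose PRU < 100, the 8 h status scores any fall of more than 5% between two single readings as YES; the margin is unjustified and could dilute the comparison with placebo

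*SAP*

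**What the plan says.** SAP 11.1.1 gives the purpose of the 8 h variable: to "estimate the proportion of subjects still with a low value of platelet aggregation 8 hours after administration of study drug". It explains that a subject who starts below 100 and is below 100 at 8 h should not be counted among those "with still significantly low platelet aggregation after study drug administration" unless the 8 h value is lower than baseline, and that the definition is changed "to be consistent with the intent of assessing back to normal/baseline value".

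The SAP then states the rule in three ways:

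- **Algorithm, 6.8.2.1:** YES if baseline PRU >= 100 and PRU at 8 h < 100, or if baseline PRU < 100 and PRU at 8 h < 0.95 x baseline.
- **Endpoint bullet, 6.8.2.1:** PRU < 100 at 8 h, or below 0.95 x baseline "if PRU baseline < 100 (i.e., platelet aggregation status 8 hours after study drug administration". Here the baseline condition qualifies only the second limb.
- **Final definition, 11.1.1:** "PRU value < 100 or < 0.95 × baseline value", with no baseline condition.

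On the readings, SAP 10.2.2 says "Baseline is the last non-missing assessment performed or value measured before or on the day and time of study drug administration", which is one value. Protocol 7.2.3.1.1 takes one VerifyNow sample per time point, whereas the duplicate LTA results are averaged (SAP 6.8.2.1). SAP 6.8.2.2 analyses the status by logistic regression against placebo, with the randomization PRU stratum as a factor, and plots the proportions as bar charts.

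**The concern.** A subject who has returned exactly to a low baseline should be scored NO. Under the algorithm, that subject is scored YES whenever the second reading happens to fall more than 5% below the first. At baseline 60 the margin is 3 PRU, and at baseline 20 it is 1 PRU. Nothing in either document shows that VerifyNow can resolve such differences. Protocol 3.2 says only that it is more standardized and less variable than LTA.

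The group affected may be large. Subjects stay on their background P2Y12 antagonists (Protocol 5.2.3), and the sample size assumes that half of placebo subjects meet a response that requires PRU < 100 from 30 minutes to 4 hours.

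At stake is the readability of the offset result: how many subjects are still inhibited at 8 h, and how each dose compares with placebo on that.

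**Working it through.** The plan states no error rate for this rule, so there is no figure of its own to reproduce.

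**Inputs**
- Margin f = 0.95 (SAP 6.8.2.1).
- One baseline reading and one 8 h reading (SAP 10.2.2, Protocol 7.2.3.1.1).
- Within-subject CV per reading: not given. Assumed range 2-10%, with larger values as a check.
- Share of subjects with pre-dose PRU < 100: not given. Assumed 25-50%. The upper end is inferred from the 50% placebo response in Protocol 10.5.

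**Step 1: chance of YES with no true change.** With independent normal errors of constant CV around the same true value,

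P(YES) = Phi( -(1 - f) / (CV x sqrt(1 + f^2)) ), where sqrt(1 + 0.95^2) = 1.379.

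| CV per reading | 0.05 / (CV x 1.379) | P(YES) |
|---|---|---|
| 2% | 1.81 | 3.5% |
| 3% | 1.21 | 11.3% |
| 5% | 0.725 | 23.4% |
| 10% | 0.363 | 35.8% |
| 20% | 0.181 | 42.8% |

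The rate is below 10% only if the CV is under about 2.8%, and exceeds 20% once the CV passes about 4.3%.

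**Step 2: selection on the observed baseline.** A simulation of 1,000,000 subjects, keeping those with observed baseline < 100 and rounding PRU to whole units, used two assumed distributions of true PRU: uniform from 5 to 300, and a half-and-half mixture of N(60, 30) and N(220, 40). It gave 4-5% at CV 2%, 11-12% at 3%, 22-23% at 5% and 33% at 10%. With a constant SD of 5 PRU the rate was about 34%. In the baseline >= 100 branch, noise alone gave only about 1-3% at CV 5-10%.

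**Step 3: effect on a whole arm** (share below 100 x P(YES)).
- CV 2%: 0.25 x 3.5% = 0.9% to 0.50 x 3.5% = 1.8%.
- CV 5%: 0.25 x 23.4% = 5.9% to 0.50 x 23.4% = 11.7%.
- CV 10%: 0.25 x 35.8% = 9.0% to 0.50 x 35.8% = 17.9%.

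**Step 4: dilution, on assumed rates.** Suppose true YES rates of 1% on placebo and 10% on active in the >= 100 branch: odds ratio (0.10/0.90)/(0.01/0.99) = 11. Add a group below 100 with no residual effect and 23.4% YES in both arms.
- Half the subjects below 100: placebo 0.5 x 1% + 0.5 x 23.4% = 12.2%; active 0.5 x 10% + 0.5 x 23.4% = 16.7%; crude odds ratio 1.4.
- A quarter below 100: 6.6% and 13.4%; crude odds ratio 2.2.

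Adjustment for the PRU stratum does not isolate the problem, because the lowest stratum is PRU < 150 and so contains subjects from both branches.

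**Step 5: the other two wordings.** If baseline is below 100, then 0.95 x baseline is below 95. Under the 11.1.1 definition, or a literal reading of the bullet, every such subject with PRU < 100 at 8 h is already YES and the 0.95 limb never decides the call. The noise calculation therefore belongs to the algorithm only. Those wordings would instead score an unchanged low-baseline subject YES almost by definition, which 11.1.1 itself says is not sensible. The 11.1.1 definition would also count any fall of more than 5% from a high baseline.

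**The case against.** The strongest reply is that the size of the problem rests on a CV that the documents do not supply. That stands. At CV 2% with a quarter of subjects below 100, noise adds under 1% to an arm. A reader might infer that a 5% fall is known to lie within assay noise, or that the false-YES rate is close to one half at any realistic variability. The documents do not support the first, and the calculation does not support the second: 23% at CV 5%, and 43% even at 20%.

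A reader might also set these rates against Protocol 5.1.1, where the high dose "provides IPA of at least 85% in no more than 5% of the subjects at 8 h". That is a dose-selection statement about IPA of at least 85%, drawn from an earlier study and modelling. It is not a limit for this status, and nothing in the plan tests the status against 5%.

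Noise calls arise in all arms and the model compares with placebo, so they cannot by themselves produce an apparent drug effect. Nor are placebo subjects untreated: they continue background antiplatelet therapy, and a background dose taken between the two samples could also lower PRU.

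Finally, absolute PRU is already summarized at each time point and modelled up to 8 h, so the binary status is not the only view of recovery. What is missing is a split at baseline 100. SAP 11.1.1 extended the status to low-baseline subjects on purpose, which argues against simply dropping them.

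**Conclusion.** The point holds conditionally. The algorithm in SAP 6.8.2.1 scores a fall of under 5 PRU, taken from two single readings, as YES, without any stated repeatability or reason for the margin. For an assumed CV of 5-10%, roughly a quarter to a third of unchanged low-baseline subjects would be misclassified in every arm. The noise contribution to an arm is about 6-18% if 25-50% of subjects start below 100; at CV 2% it is about 1-2%. The consequence is inflated proportions and a weaker contrast with placebo on a non-primary endpoint of an exploratory study. The primary PD response is untouched. Separately, and with no assumption about CV, the three statements of the variable in the SAP do not agree.

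**What to change.** 1. Present the 8 h status table, bar charts and logistic model separately for pre-dose PRU >= 100, where PRU < 100 at 8 h is the criterion, and for pre-dose PRU < 100. Name the >= 100 group as the main 8 h offset result.
2. For pre-dose PRU < 100, report PRU at 8 h minus pre-dose PRU by arm, with the difference from placebo and its CI.
3. If a binary status is kept for that group, set its margin from PRU repeatability and state the source. For illustration, a required fall of 10% gives 6.9% false YES at CV 5%, 20% gives 5.9% at CV 10%, and 30% gives 5.1% at CV 15%. Averaging two pre-dose readings while keeping 0.95 helps little: 20% at CV 5% and 34% at CV 10%.
4. Reconcile the 6.8.2.1 algorithm, the 6.8.2.1 bullet and the 11.1.1 definition so that one rule remains, with its baseline condition explicit.

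The cost is SAP wording and smaller denominators in each part; no new data are needed. In the < 100 part the randomization stratum drops out of the model, since all these subjects are in the PRU < 150 stratum. In the >= 100 part placebo events may be very few (with 54 of 108 placebo subjects there, 1-3% is about one), so give the difference in proportions with its CI alongside the logistic result.

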6.8.3 Handling of missing data

Subjects for whom determination of the PD response is not possible will not be included in the computation of response rate for the main analysis, however they will be counted as non-responders in the sensitivity analysis.

No other imputations are planned.

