8 GENERAL STATISTICAL METHODOLOGY

Data will be analyzed using SAS version 9.3 or higher.

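### The 8 h platelet aggregation status counts a subject with no 8 h PRU as no longer inhibited, because its algorithm has no missing-value condition (minor)

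*SAP*

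**What the plan says.** SAP 6.8.2.1 states that the 8 h status "variable is defined as binary with value determined as per the following algorithm". The status is YES in two cases: baseline PRU is at least 100 and the 8 h PRU is below 100, or baseline PRU is below 100 and the 8 h PRU is below 0.95 times baseline. All other cases fall to "ELSE status = NO".

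SAP 11.1.1 gives the purpose: "The intent of this variable was to estimate the proportion of subjects still with a low value of platelet aggregation 8 hours after administration". YES therefore means still inhibited, and NO means not still inhibited.

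Two neighbouring variables in 6.8.2.1 do deal with missing data. LTA-PD response carries the condition "AND none is missing". For IPA-V the text says "All analyses conducted on this variable will exclude missing values".

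SAP 6.8.3 gives a rule for subjects whose PD response (the primary endpoint) cannot be determined, then adds "No other imputations are planned". SAP 8.1.2 leaves missing values out of percentage denominators by default. Under SAP 6.8.2.2 the 8 h status feeds a logistic regression against placebo and bar charts.

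**The concern.** A subject with no 8 h sample tells us nothing about whether inhibition has worn off by 8 h. The algorithm nevertheless gives that subject a definite answer, and the answer is the one that favours offset. In the primary endpoint the same closing branch means non-responder, which is cautious for an active arm. Here it lowers the residual-inhibition rate.

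The derived status can never be missing, so the general rules that would normally remove such a subject have nothing to work on. The figures at stake are the 8 h proportion in each arm, the bar charts and the logistic model.

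**Working it through.** **Does anything else in the plan catch the case?**

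- SAP 6.8.3: its explicit rule covers PD response only. Its closing sentence rules out other imputations, which conflicts with scoring an absent value NO.
- SAP 8.1.2: it removes missing values from denominators, but this status is never missing.
- SAP Appendix B, Table 7: a missing 8 h VerifyNow sample excludes a subject from the per-protocol set. SAP Table 2, however, analyses other PD endpoints on the FAS only, and SAP 6.8.2.3 plans no sensitivity analysis for them.

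None of these reaches the variable.

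**What the algorithm returns.** It was coded twice: once with a comparison on a missing value treated as false (the plain reading), and once with a missing number sorted below every number (SAS ordering).

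| Baseline PRU | 8 h PRU | Plain reading | SAS ordering |
|---|---|---|---|
| 200 | missing | NO | YES |
| 80 | missing | NO | YES |
| missing | 50 | NO | NO |
| 200 | 50 | YES | YES |
| 200 | 180 | NO | NO |

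No input returns missing. Under SAS ordering the YES arises at any non-missing baseline, because a missing 8 h value is below both 100 and 0.95 × baseline.

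**Size.** The documents state no expected figure for this status, so there is none to reproduce. The denominator is the planned arm size in Protocol 10.5: 98 × 1.10 = 107.8, that is 108. Let t be the YES rate among subjects with an 8 h value and m the share without one. Both are assumptions.

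- Missing excluded: reported rate = t.
- Plain reading: reported rate = t(1-m), a drop of t·m.
- Unguarded SAS code: reported rate = t(1-m) + m, a rise of m(1-t).

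| t | m | Excluded | Plain reading | Unguarded SAS |
|---|---|---|---|---|
| 5% | 5% | 5.0% | 0.05 × 0.95 = 4.8% | 4.75% + 5% = 9.8% |
| 5% | 10% | 5.0% | 0.05 × 0.90 = 4.5% | 4.5% + 10% = 14.5% |
| 20% | 10% | 20.0% | 0.20 × 0.90 = 18.0% | 18% + 10% = 28.0% |

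In subjects, with 108 in the arm, 5 missing and t = 5%: 103 × 0.05 = 5.15 expected YES. That gives 5.15/103 = 5.0% if the missing are excluded, 5.15/108 = 4.8% on the plain reading, and (5.15 + 5)/108 = 9.4% under unguarded SAS code.

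**Logistic model, crude odds ratio.** Assume 20% on active, 2% on placebo and m = 5% in both arms.

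- Excluded: (0.20/0.80)/(0.02/0.98) = 12.3.
- Plain reading, rates 19.0% and 1.9%: (0.190/0.810)/(0.019/0.981) = 12.1.
- Unguarded SAS, rates 24.0% and 6.9%: (0.240/0.760)/(0.069/0.931) = 4.3.

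**The case against.** The best defence is that exclusion was plainly intended. The primary PD response algorithm in SAP 6.8.1.1 also ends in a catch-all NO, yet 6.8.3 takes undeterminable subjects out of the main response rate. The catch-all is therefore not reliably this plan's last word on missing data, and 6.8.3 and 8.1.2 both lean towards exclusion. This stands as evidence of intent. It does not remove the conflict, because for the 8 h status the written branch is explicit and no sentence overrides it.

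A second defence also stands: the literal effect is slight, half a percentage point at t = 5% and m = 10%. A third is that absolute PRU is summarised by time point with missing counts shown, and individual data are listed, so absent 8 h values would be visible elsewhere. The status table itself would still show none missing.

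Four stronger readings are tempting, and the documents do not support them.

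- **That the bias moves a pass/fail figure for the high dose.** Protocol 5.1.1 says the high dose "provides IPA of at least 85% in no more than 5% of the subjects at 8 h". That is a reason for choosing the dose, based on the healthy-subject study and modelling and stated as IPA of at least 85%. The status uses PRU below 100 (or a fall below baseline) in patients with CAD. No section applies 5% to it as a criterion.
- **That the plan scores missing as still inhibited.** SAP section 8 says "Data will be analyzed using SAS version 9.3 or higher", and a missing number does sort low there. But 6.8.2.1 gives logic, not code. The YES result needs an unguarded comparison that also escapes checking, and SAP Appendix E records updates after two dry-run reviews.
- **That 10% is the plan's missing rate at 8 h.** Protocol 10.5 uses about 10% for drop-out or non-evaluable primary endpoint data, which draw on several time points. For a single 8 h sample it is a borrowed and probably high value.
- **That a missing baseline is a comparable problem.** Protocol 5.1.3.1 requires the pre-dose VerifyNow result for stratified randomization, and SAP 10.2.2 takes the last non-missing value before dosing. The case should hardly arise.

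**Conclusion.** The point holds at minor severity. As written, the 8 h status scores a missing 8 h PRU as NO. This contradicts the statement that no other imputations are planned and keeps the general denominator rule from acting. The literal result is a small shift towards apparent offset, equal to t·m: about 0.25 points at t = 5% and m = 5%, and 2 points at t = 20% and m = 10%. Calling the shift a bias presumes that subjects without a value would resemble those with one.

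The larger upward shift under unguarded SAS code is a risk of implementation. It matters mainly because two programmers working from the same text could produce different tables. The variable is one of the other PD endpoints, so the primary tests and the sample size are not affected.

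**What to change.** In SAP 6.8.2.1, before the IF, add: if the 8 h PRU (or the baseline PRU) is missing, the status is missing and the subject is left out of the proportion, the bar charts and the logistic model. Report the number with missing status per arm next to the proportion. A further row scoring missing as YES, as an upper bound on residual inhibition, is optional.

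The cost is one line in the algorithm and one table row, or two with the bound. No new data and no change to the primary analysis are needed.
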